1. DESCRIPTION OF THE PROJECT

1.1 Rationale and objectives of the study

1.1.1 Rationale

Despite global efforts to decrease discomfort during surgical abortion, pain remains a limiting factor in where and how abortions are performed. My primary fellowship research project focused on utilizing a self-administered lidocaine gel to decrease pain with first trimester surgical abortion, and found that there was no difference in pain level (as measured by VAS score) at time of cervical dilation between women randomized to the standard paracervical block group versus the lidocaine gel only group. Given that pain remains a limiting barrier for other gynecologic office procedures as well, we decided to apply this method of analgesia to intrauterine device (IUD) insertions.

For these procedures no standardized clinical guidelines for pain management exist. Reducing pain associated with IUD insertion may benefit patients and providers. When patients are comfortable during their procedure, it is likely the provider can more quickly and with fewer complications perform the insertion. It could also be argued these patients would report higher satisfaction with their procedure and provider [Kass-Wolf & Fisher, 2014]. To our knowledge, there is limited clinical consensus on pain management guidelines, demonstrating value in researching potential pain management solutions.

We propose to explore the effect of a locally applied vaginal lidocaine gel in place of the standard of care pain management (i.e. paracervical block or no intervention respectively) prior to IUD insertions.

SALUD (IUD insertion): We hypothesize that lidocaine gel is superior to placebo at decreasing procedural pain at a variety of time points throughout the procedure. This is a superiority, blinded, randomized controlled trial.

If self-administered vaginal gel is acceptable and effective, it would increase options for pain control during abortion and other gynecologic procedures (IUD insertion).

1.1.2 Objectives and hypotheses

The objective of this study is to compare pain control at various time points during IUD insertions using a locally applied, patient-administered lidocaine gel as compared to standard of care (i.e. no pre-procedural analgesia).

If a patient-administered vaginal gel is acceptable and effective, it would increase options for pain control during these gynecologic procedures.

Hypothesis: Patients who receive 20 mL of 2% lidocaine gel self-administered 20-30 minutes prior to IUD procedures will have pain control superior to that of a placebo gel.

Primary Outcomes

- SALUD (IUD Insertion): Pain perceived by Visual Analogue Scale (0-100 mm) at the time of speculum removal

Secondary Outcomes

- Pain perceived at additional time points during/after the procedure:
 - Anticipated pain: measured upon clinic intake
 - Baseline pain: upon arrival to procedure room
 - After speculum placement
 - After tenaculum placement

Note: The research coordinator will stand at the head of the bed beside the patient with an iPad that has an enlarged VAS on it. They will ask the patient to tap somewhere along the VAS at these various time points to indicate their respective pain score.

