1.3 Design and methodology

1.3.1 Research design and General Methodological Approach

This is a superiority, blinded, randomized controlled trial of women ages 18 and older undergoing elective IUD insertion. We chose a superiority approach based on the most commonly practiced method for pain management in these procedures (no intervention). In this study, participants and health care professionals will be blinded from the intervention/study group. Standard lubricating gel has the same clear gel appearance as lidocaine gel and will be used to ensure blinding. Due to logistical barriers with needing to prepare the gel immediately prior to insertion, the research coordinator responsible for enrolling and randomizing participants will not be blind to the intervention.

Participants will be recruited from Stanford Gynecology Clinic. Informed consent will be obtained prior to enrollment by a trained research coordinator after which, patients will be randomized to either group by block randomization. At the completion of the procedure, compensation will be given in the form of a \$15 Target Gift Card or a \$15 donation to a fund that assists low-income women obtain family planning services.

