1.3.6 Follow-up procedure

There is no extended follow-up planned for this study. Subjects will complete a survey at the completion of the procedure asking them to give a final pain score (secondary outcome) and assessment of overall acceptability (likelihood to recommend procedure or choose this form of pain control again). Any potential procedural complications will be managed using typical standard of care procedures for this clinic.

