1.3.10 Data analysis

SAS Version 9.3 and SPSS Version 23.0 will be used for data analysis.

Statistical Methods:

- Demographic characteristics will be examined among the randomized groups using Fisher's exact test
- Median VAS pain scores will be analyzed with Student's *t*-tests and non-parametric tests, respectively
- Linear regression may be completed in multivariate analysis to identify predictors of pain in an exploratory analysis

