1.3.11 Number of subjects and statistical power

SALUD (IUD Insertion): The following power calculation accounts for continuous outcomes in a superiority trial

$$n = f(\alpha/2, \beta) \times 2 \times \sigma^2 / (\mu_1 - \mu_2)^2$$

- Effect size = 15% difference in VAS [Jensen 2003, Todd 1996, Rowbothom 2001]

- Mean outcome in control group: 36.7mm [Allen 2013]
- Standard deviation of VAS = 21.7mm [Allen 2013]
- Assuming $\alpha = 0.025$, $\beta = 0.10$, 90% power

SUMMARY: 200 patients are required to have a 90% chance of detecting, as significant at the 2.5% level, a decrease in the primary outcome measure from 36.7 in the control group to 21.7 in the experimental group. Accounting for drop-outs and protocol deviations by adding 10% to the number of participants, the total enrollment will be 220.

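### Anticipated pain, scored at intake, is filed as a secondary outcome when it should be a pre-specified covariate in the primary comparison

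*Combined protocol and SAP*

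**What the plan says.** Section 1.1.2 names one primary outcome, the VAS score (0-100 mm) when the speculum is removed. Under secondary outcomes it has the heading "Pain perceived at additional time points during/after the procedure" and four scores beneath it. The first is "Anticipated pain: measured upon clinic intake"; the second is "Baseline pain: upon arrival to procedure room"; the other two follow speculum and tenaculum placement. Section 1.3.6 adds an end-of-procedure survey in which patients "give a final pain score (secondary outcome").

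Section 1.3.10 states that "Median VAS pain scores will be analyzed with" t-tests and non-parametric tests, and names no covariate. The only model it mentions is optional: "Linear regression may be completed in multivariate analysis to identify predictors of pain in an exploratory analysis". No other section names a covariate for the primary comparison, and the sample size in section 1.3.11 uses the raw SD.

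On timing, section 1.3.4 has the gel self-administered 20 to 30 minutes before the procedure starts. Sections 1.3.1 and 1.3.3 put consent before randomisation. No section places clinic intake in that sequence. Section 1.3.1 also says that "the research coordinator responsible for enrolling and randomizing participants will not be blind to the intervention", and the note in section 1.1.2 has the research coordinator collect the VAS scores.

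**The concern.** A score recorded before treatment carries no information about the treatment effect when analysed as an outcome. Any difference between arms in anticipated pain would be chance, yet its place in the outcome list invites a between-arm test and a reading of the result as efficacy, although the plan does not spell out such a test. The score also fits poorly under its own heading, since intake is neither during nor after the procedure.

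Its natural use is to explain variation between patients in the primary outcome. If patients who expect more pain tend to report more, adjusting for that expectation narrows the interval around the treatment effect and removes the effect of a chance imbalance between arms. The documents describe block randomisation with no stratification, so nothing in the design handles such an imbalance. Because regression is only optional, an adjusted result could also be reported or left out after the data are seen.

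**Working it through.** **Inputs from section 1.3.11.** SD 21.7 mm; planned difference 36.7 - 21.7 = 15 mm; alpha 0.025, entered in the formula as alpha/2 and so literally two-sided 2.5%; power 90%; 200 patients before the drop-out allowance. I take 100 per arm: the ratio is not stated in words, but the factor 2 in the formula implies equal arms.

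**Assumption.** r is the correlation of anticipated pain with the primary VAS. The documents do not give it. I use 0.2 to 0.5.

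**The plan's own figure.** With the section's formula, n per arm = (2.241 + 1.282)² × 2 × 21.7² / 15² = 52, or 104 in total. At two-sided 5% it is 44 per arm, or 88 in total. The plan says "200 patients are required to have a 90% chance of detecting, as significant at the 2.5% level", which these inputs do not reproduce. That is a separate matter. What counts here is that 200 patients give 99.6% power at 15 mm on the stated inputs.

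**Effect of adjustment.**

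- SE = 21.7 × √(2/100) × √(1 - r²)
- 95% CI half-width = 1.96 × SE
- Difference detectable with 90% power = (2.241 + 1.282) × SE at two-sided 2.5%, or (1.960 + 1.282) × SE at two-sided 5%
- Power for difference d at two-sided 2.5% = Φ(d/SE - 2.241)

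| | r = 0 (unadjusted) | r = 0.2 | r = 0.3 | r = 0.5 |
|---|---|---|---|---|
| Fall in variance (r²) | 0% | 4% | 9% | 25% |
| SE, mm | 3.07 | 3.01 | 2.93 | 2.66 |
| 95% CI half-width, mm | 6.0 | 5.9 | 5.7 | 5.2 |
| Detectable difference, two-sided 2.5%, mm | 10.8 | 10.6 | 10.3 | 9.4 |
| Detectable difference, two-sided 5%, mm | 9.9 | 9.7 | 9.5 | 8.6 |
| Power at 15 mm | 99.6% | 99.7% | 99.8% | 99.97% |
| Power at 10 mm | 84.5% | 86.1% | 88.0% | 93.6% |
| Unadjusted patients giving the same precision, 200/(1 - r²) | 200 | 208 | 220 | 267 |

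**Chance imbalance.** If the arms differ in anticipated pain by one standard error, the unadjusted estimate shifts by r × 3.07 mm: 0.6 mm at r = 0.2, 0.9 mm at 0.3 and 1.5 mm at 0.5. Adjustment removes this shift. It is the same gain as in the table, seen in a single trial, and should not be counted twice.

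**Cost if the score is not prognostic.** With r = 0, estimating one extra coefficient gives SE = 3.069 × √(1 + 1/196) = 3.08 mm, against 3.07 mm unadjusted.

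**The case against.** The strongest reply is that nothing here is wrong: an unadjusted test in a randomised trial is valid, and at the difference the trial was sized for power is already near 100%. The visible gain is at 10 mm, a figure that is not in the plan. The size of the gain rests wholly on r, and an expectation of pain is not a pre-treatment measurement of the outcome, so a high r cannot be presumed; at r = 0.1 the SE falls by only 0.5%. All of this stands, and it limits the point to one of efficiency. It does not remove the case for adjusting. Section 1.2 reports two earlier trials of 2% lidocaine gel with no significant difference from placebo, so an effect below 15 mm is a realistic possibility, and the cost at r = 0 is 0.01 mm on the SE.

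A second reply is that the scores may be skewed: section 1.3.11 implies a mean of 21.7 mm and an SD of 21.7 mm in the lidocaine arm, on a scale bounded at zero. ANCOVA would then put a model of means ahead of the planned non-parametric test. With 100 per arm a comparison of means is defensible, and the non-parametric test can stay as a sensitivity analysis.

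A third is timing. Since the documents do not say whether intake scoring precedes randomisation, requiring that order might change clinic workflow as well as wording. That is fair, but the change would be to when one existing question is asked.

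**Conclusion.** The concern holds, as a recommended improvement and not as an error that threatens validity. Anticipated pain is misplaced as an outcome whatever r is. Using it as a covariate would cut the SE by 2% to 13% for an assumed r of 0.2 to 0.5. The benefit is a somewhat tighter interval and better power if the true effect is smaller than 15 mm. At the low end of that range it is small.

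The figures assume SD 21.7 mm, 100 analysed per arm, a linear relation with equal variance in the two arms, and a score recorded before the gel. That order is very likely but not stated.

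**What to change.** **Section 1.1.2.** Move anticipated pain from the secondary outcomes to the baseline characteristics, and state that it is recorded before randomisation. The order matters because the coordinator who randomises is unblinded and also collects the scores.

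**Section 1.3.10.**

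- Pre-specify the primary analysis as ANCOVA of VAS at speculum removal on arm and anticipated pain.
- Keep the unadjusted t-test and the non-parametric test as sensitivity analyses.
- For a missing intake score, substitute the overall mean across both arms and keep the patient in the analysis.
- Do not adjust for baseline pain on arrival in the procedure room unless it is shown to be recorded before the gel. Its order is not stated, and a score taken after the gel could already carry a treatment effect.
- Keep the exploratory regression for predictors of pain separate from this model.

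**Cost.** Wording in two sections, a missing-covariate rule and a little more analysis. No extra patients, staff or assessments are needed; at most, the intake question is moved ahead of randomisation if it is not there already. The primary test becomes model-based instead of rank-based.

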1.2 Previous similar studies

While several previous studies have evaluated possible interventions for reducing IUD insertion pain, few have shown promising results. Although many providers recommend that patients take nonsteroidal anti-inflammatory drugs (NSAIDs) prior to the procedure, a 2009 Cochrane review concluded that NSAIDs are not effective at reducing pain during IUD insertion. The same review also concluded that the use of misoprostol to soften and open the cervix does not effectively reduce peri-insertional pain during insertion in nulliparous women, and may cause side effects. In a randomized trial, a 1% lidocaine paracervical block did not significantly decrease perceived pain with IUD insertion [Mody, 2012]. Randomized controlled trials by Allen et al. and McNicholas et al. examined the effect of 2% cervical lidocaine gel applied 3 minutes prior to the procedure. Both studies found no significant differences in pain scores with IUD insertion or tenaculum placement when compared with placebo.

To the best of our knowledge, there is no published data that 1) rigorously examines the effects of a prolonged time interval between local anesthetic administration and IUD insertion, or 2) explores whether adequate pain relief is possible through self-administered, non-invasive means alone.

In a soon to be published study conducted at Stanford (my primary fellowship project), self-administration of 20 ml of 2% lidocaine gel 20-30 minutes prior to first trimester surgical abortion was shown to be non-inferior to a traditional paracervical lidocaine block as a pain control approach. Given these promising results, we propose to

evaluate the effect of 2% lidocaine gel self-administered 20-30 minutes prior to IUD insertion in place of the standard of care pain management (i.e, no intervention).

1.3 Design and methodology

1.3.1 Research design and General Methodological Approach

This is a superiority, blinded, randomized controlled trial of women ages 18 and older undergoing elective IUD insertion. We chose a superiority approach based on the most commonly practiced method for pain management in these procedures (no intervention). In this study, participants and health care professionals will be blinded from the intervention/study group. Standard lubricating gel has the same clear gel appearance as lidocaine gel and will be used to ensure blinding. Due to logistical barriers with needing to prepare the gel immediately prior to insertion, the research coordinator responsible for enrolling and randomizing participants will not be blind to the intervention.

Participants will be recruited from Stanford Gynecology Clinic. Informed consent will be obtained prior to enrollment by a trained research coordinator after which, patients will be randomized to either group by block randomization. At the completion of the procedure, compensation will be given in the form of a \$15 Target Gift Card or a \$15 donation to a fund that assists low-income women obtain family planning services.

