1.3.3 Subject Recruitment and Allocation

Potential participants will be identified for recruitment if scheduled for IUD insertion (regardless of type) at the Stanford University Gynecology Clinic. They will be approached by the research coordinator or study investigator and consented for the study. If enrolled, they will be randomized by block randomization. The research coordinator will prepare a 20ml pre-filled syringe with either 2% lidocaine gel or placebo, so that the physician/researcher is blinded to the group allocated. Participants will receive the treatment previously allocated on a rolling bases. The patient and provider will be blinded as to the treatment group.

All patients will then receive instruction on how to properly self-insert the study medication using a pictorial guide as previously employed in a similar RCT at this site (SALSA).

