1.3.12 Study limitations

The potential limitations of this study include inability to blind the research coordinator given the need for preparation of the gel immediately prior to the patient's self-insertion, and the fact that this is a single site out-patient clinic at a university setting, that may not reach as widely as is desirable for the purposes of generalizability.

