1.3.13 Duration of project

There are currently around 50 IUD insertions performed each month at the Stanford Gynecology Clinic, however we are tripling our IUD access clinics starting in July, so we anticipate over 100 IUD procedures per month. Estimating 30% enrollment, the anticipated length of the study is 7-10 months.

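### The unblinded coordinator enrols patients and randomises them in blocks, so the next arm can be partly predicted, and the available text describes no allocation concealment

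*Combined protocol and SAP*

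**What the plan says.** Section 1.3.1 states that "the research coordinator responsible for enrolling and randomizing participants will not be blind to the intervention". Consent comes first, "after which, patients will be randomized to either group by block randomization". Section 1.3.3 repeats the block method and adds three facts:

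- On recruitment: "They will be approached by the research coordinator or study investigator and consented for the study".
- On preparation: "The research coordinator will prepare a 20ml pre-filled syringe with either 2% lidocaine gel or placebo". The stated aim is to keep the clinician or researcher unaware of the arm.
- On the order of allocation: "Participants will receive the treatment previously allocated on a rolling bases".

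Section 1.3.12 lists the coordinator's lack of blinding as a limitation ("inability to blind the research coordinator given the need for preparation of the gel immediately prior"), but does not mention predictability of the next assignment. Neither 1.3.1 nor 1.3.3 gives a block size, says whether blocks vary, names who generates or holds the sequence, or says how the next arm is hidden until a patient is enrolled. REDCap appears only for data capture and management (1.3.9, 1.4). Section 1.3.5 is not in the available text.

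**The concern.** Blinding and concealment are different protections. Identical-looking gel keeps the patient and provider from knowing the arm after assignment. Concealment keeps the recruiter from knowing the arm before assignment. Here the recruiter fills each syringe and so can know every earlier arm at a single clinic. Blocks force the arms back to balance, so past arms carry information about the next one.

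At stake is selection bias. Whom the coordinator approaches, or how consent is pursued, could depend on the arm expected next. Consent before randomisation does not prevent this, because the decision to approach comes earlier still.

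There is some room for selection. Section 1.3.13 says: "Estimating 30% enrollment, the anticipated length of the study is 7-10 months". Section 1.3.10 offers no firm protection at analysis either: regression is optional and exploratory.

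**Working it through.** The plan gives no figure for predictability, so there is nothing of its own to reproduce. Inputs from the documents: block randomisation (1.3.1, 1.3.3), 220 enrolled, 200 in the power statement, SD 21.7 mm and a 2.5% level (1.3.11), 30% enrolment (1.3.13). Assumptions: 1:1 allocation, a recruiter who knows all past arms, the 2.5% level read as two-sided and, in step 1, fixed blocks of known size.

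**1. Fixed blocks.** The best guess is the arm with more places left in the block; a tie counts as 1/2. For blocks of 4, the chance of a correct guess is 1/2 at slot 1 and 2/3 at slot 2. At slot 3 it is (1/3)(1) + (2/3)(1/2) = 2/3, and at slot 4 it is 1. The mean is (1/2 + 2/3 + 2/3 + 1)/4 = 17/24 = 70.8%. The certain slots are (1/3 + 1)/4 = 33.3%. The same enumeration gives:

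| Block size | Guessed correctly | Certain | Certain, of 220 |
|---|---|---|---|
| 2 | 75.0% | 50.0% | 110 |
| 4 | 70.8% | 33.3% | about 73 |
| 6 | 68.3% | 25.0% | 55 |
| 8 | 66.6% | 20.0% | 44 |
| 10 | 65.3% | 16.7% | about 37 |
| 20 | 61.7% | 9.1% | 20 |

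**2. Varying blocks of unknown size.** Simulation, guessing the arm with fewer patients so far, gives 69% correct for sizes 4/6 and 68% for 4/6/8. Varying the size alone does little when the recruiter sees every past arm.

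**3. Room for selection.** 220/0.30 = about 733 insertions, and 733 − 220 = 513 women not enrolled. This is an upper limit: it includes ineligible women and decliners, whom the documents do not count separately.

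**4. Illustration of scale, not a prediction.** Suppose every predictable slot is steered, with patients d mm below average for one arm and d mm above for the other. If g is the guess rate, each arm shifts by (2g − 1)d in opposite directions, so the bias is 2(2g − 1)d.

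- Standard error with 100 per arm: 21.7 × √(2/100) = 3.069 mm.
- Smallest significant difference at two-sided 2.5%: 2.241 × 3.069 = about 6.9 mm.
- Blocks of 4: bias = 2(2 × 0.7083 − 1)d = 0.833d, so d = 6.88/0.833 = about 8.3 mm.
- Blocks of 2: factor 1.0, d = about 6.9 mm. Blocks of 10: factor 0.613, d = about 11.2 mm. Blocks of 20: factor 0.468, d = about 14.7 mm.

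At these values of d, and with no true effect, the expected difference sits at the significance limit.

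**5. Cost of simple randomisation.** For Binomial(200, 0.5), the 2.5% and 97.5% points are 86 and 114. Relative efficiency at that limit is 4 × 86 × 114/200² = 0.980. The standard error is 21.7 × √(1/86 + 1/114) = 3.099 mm. Power moves from 99.6% to 99.5% for 15 mm, and from 84.5% to 83.8% for an assumed 10 mm.

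**The case against.** The strongest reply is that silence is not a defect. The text does not say that the list is visible or the block size known. The reference to treatment previously allocated fits a sequence made in advance, and a method may be described in text that is not available. The unblinded coordinator is disclosed twice, the patient and provider are blinded, and the patient taps her own score. Nothing shows that the coordinator can judge a woman's likely pain before approaching her.

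Part of this stands. A reader might infer that the coordinator reads the list or that selective enrolment will occur; the documents support neither. A reader might also treat all 513 women as open to discretion, but the number is only a ceiling. Nor does the risk cover every patient, because 1.3.3 lets the investigator recruit too.

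The central point survives. Even a perfectly hidden list does not stop guessing from past arms, and every block size tried is partly predictable.

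It may also be tempting to argue that the coordinator's prompting for VAS scores (1.1.2) biases the primary outcome. The note follows the list of secondary time points, so extending it to the score at speculum removal is an inference. The patient is blinded and enters the score herself, and nothing in the documents quantifies an effect. That argument is not relied on here.

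**Conclusion.** The concern holds as a risk built into the procedure as written. For patients the coordinator recruits, about 62% to 75% of assignments can be guessed with known fixed blocks of 20 down to 2, and 68% to 69% with the varying sizes tried, against 50% by chance. These rates rest on 1:1 allocation and one recruiter seeing all past arms; the fixed-block rates also assume that the size is known.

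The bias in mm and its direction cannot be determined from the documents; it could favour either arm. A reader might infer that steering would produce the planned 15 mm difference, or that it is too weak to do so. Neither follows: the answer depends on the unstated block size and on how far steered patients differ from average. The illustration shows only that a significant result would need much less than 15 mm. The plan should be changed, with medium confidence about the practical effect.

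**What to change.** 1. **Hide the sequence.** Have it generated and held by someone who does not recruit, hidden from recruiting staff. Release each arm only after consent, eligibility and the anticipated-pain score are recorded. REDCap could do this if its allocation function is available; the documents describe it only for data capture and management. The cost is set-up, access rights and a named sequence holder. This stops reading ahead but not guessing.

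2. **Use simple 1:1 randomisation instead of blocks.** The coordinator must see each released arm to fill the syringe, and simple randomisation brings the guess rate to 50%. The cost is chance imbalance (95% of splits within 86:114 of 200, under 1 percentage point of power at that limit) and loss of enforced balance over calendar time. The latter is relevant because 1.3.13 expects clinic volume to grow.

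3. **If blocks are kept,** have the investigator, kept blind to allocation in REDCap, do all approaching and consenting, with the coordinator only releasing the arm and filling the syringe. This costs investigator time. It also requires 1.3.1, where the coordinator obtains consent, to be reconciled with 1.3.3, and allocation to be hidden from the investigator's data-management access (1.3.9, 1.4).

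Whichever route is taken, section 1.3.3 should state the randomisation method, the sequence holder and the point of release. Any block sizes should be recorded where recruiting staff cannot see them.
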